4. DESCRIPTION OF THE PROTOCOL

ALXN1210-PNH-304 is a Phase 3, open-label, single-arm multicenter study to evaluate the PK/PD, safety, and efficacy of ALXN1210 administered by intravenous (IV) infusion to pediatric patients (< 18 years of age) with paroxysmal nocturnal hemoglobinuria (PNH). The study consists of a 4-week Screening Period, a 26-week Primary Evaluation Period, and an Extension Period.

Patients will receive a loading dose of ALXN1210 on Day 1, followed by maintenance dosing of ALXN1210 on Day 15 and q8w thereafter for patients weighing ≥ 20 kg, or q4w for patients weighing < 20 kg, as shown in Table 2. With the agreement of the Alexion Medical Monitor, the 600 mg loading dose may be given to patients weighing ≥ 5 to < 10 kg as 2 separate infusions administered no more than 24 hours apart. Dosages are based on the patient's body weight recorded on the day of dosing or the most recently recorded weight. For patients entering the study on eculizumab therapy, Day 1 of study treatment will occur 2 weeks from the patient's last dose of eculizumab.

Table 2: Loading and Maintenance Treatment Regimens

Body Weight Range (kg) ^a	Loading Dose (mg)	Maintenance Doses (mg)	Maintenance Dosing Frequency
≥ 5 to < 10	600 ^b	300	q4w
≥ 10 to < 20	600	600	q4w
≥ 20 to < 30	900	2100	q8w
≥ 30 to < 40	1200	2700	q8w
≥ 40 to < 60	2400	3000	q8w
≥ 60 to < 100	2700	3300	q8w
≥ 100	3000	3600	q8w

^a Dose regimen will be based on body weight obtained at the study visit. If the study drug needs to be prepared the night prior to the visit, the weight from the previous visit may be used.

^b With the agreement of the Alexion Medical Monitor, the 600 mg loading may be given to patients weighing ≥ 5 to < 10 kg as 2 separate infusions administered no more than 24 hours apart.

Abbreviations: q4w = once every 4 weeks; q8w = once every 8 weeks

With the agreement of the Alexion Medical Monitor, administration of a supplemental dose of ALXN1210 is permitted.

An interim analysis of data, including ALXN1210 PK and free C5 levels, will be conducted after 4 patients weighing ≥ 5 kg to < 40 kg have completed dosing through Day 71. Enrollment of patients will proceed without interruption while the analysis is ongoing. The accrued safety and PK/PD data will be assessed to ensure that ALXN1210 treatment is well tolerated and is providing adequate complement inhibition. Based on this review, the dose regimen may be adjusted. In addition, an independent Data Monitoring Committee (DMC) will review safety data from the study on a regular basis. Prior to the initiation of the study, the committee will develop a charter to describe their activities and responsibilities.

To support regulatory filings, interim analyses may be conducted based on efficacy, safety, PK, PD, and immunogenicity data collected through the end of the 26-week Primary Evaluation Period (Day 183) after 12 patients are enrolled, and after enrollment is completed.

After completion of all pre-dose assessments on Day 183, all patients will enter an Extension Period and continue to receive ALXN1210 according to the appropriate weight-based regimen. The Extension Period will continue until the product is registered or approved (in accordance with country-specific regulations) or for up to 4 years, whichever occurs first, except in Norway where the Extension Period will be 4 years. The end of study is defined as the last patient's last visit or follow-up (whether on site or via phone call) in the Extension Period.

The study objectives are as follows:

The objectives of this study are to assess the pharmacokinetics (PK), pharmacodynamics (PD), safety, and efficacy of ALXN1210 in pediatric patients with paroxysmal nocturnal hemoglobinuria (PNH). Additional information about the study can be found in the protocol.

To support regulatory filings, interim CSRs may be prepared based on efficacy, safety, PK, PD, and immunogenicity data collected through the end of the 26-week Primary Evaluation Period (Day 183) after 12 patients are enrolled, and after enrollment is completed. This statistical analysis plan (SAP) outlines only the analyses that are to be included in the report developed after the 26-week Primary Evaluation Period after 12 patients are enrolled. A final CSR to summarize long-term efficacy, safety, PK, PD, and immunogenicity parameters will be produced at study completion.

4.1. Changes From Analyses Specified in the Protocol

Not applicable

4.2. Changes From Analyses Specified in the Previous Version of the SAP

During the conduct of the phase 3 studies ALXN1210-PNH-301 and ALXN1210-PNH-302, it was observed that up to 1% of central laboratory chemistry samples undergo in vitro erythrocyte lysis or table top hemolysis (TTH) caused by sample mishandling. This is unrelated to hemolysis due to PNH. The reasons for TTH vary and include delayed or improper centrifugation and traumatic blood draws. In addition, PIGA deficient erythrocytes from patients with PNH are more susceptible to mechanical lysis than non-PNH erythrocytes (Smith, 1985). Hemolysis results in release of RBC contents including LDH, potassium, and AST. In contrast to hemolysis in patients with PNH, in which serum potassium is normal, for samples affected by TTH both potassium and LDH are markedly and proportionally increased (Goyal and Schmotzer, 2015; Ostendorp, 2006). Marked hyperkalemia (defined as $> 6\text{mmol/L}$) seen in TTH, but not PNH hemolysis, differentiates TTH (in vitro) from PNH hemolysis (in vivo), and is not clinically significant (Hollander-Rodriguez, 2006; Kovesdy, 2014). Due to the artefactual increase in LDH in samples affected by TTH, the potassium, ALT, AST, magnesium, phosphorous, and LDH values in samples affected by TTH will not be used in the analysis of any efficacy or safety endpoints, with the exception that the LDH value will be used for the qualification of breakthrough hemolysis events. Breakthrough hemolysis is captured on a separate form and central lab LDH, in addition to new or worsening symptoms as specified in the protocol, are used by the Principal Investigator or designee to qualify patients with breakthrough hemolysis. Table top hemolysis samples from the central lab will be defined as having serum potassium $\geq 6\text{mmol/L}$ and LDH $\geq 2 \times \text{ULN}$, and will be excluded from analyses as described above.

In order to be consistent with ALXN1210-PNH-301 and ALXN1210-PNH-302, patients who withdraw from the study due to lack of efficacy during the Primary Evaluation Period will be considered as non-responders in the analyses of breakthrough hemolysis, transfusion avoidance (TA), and stabilized hemoglobin. Shift tables over time will be presented for all central laboratory values, where applicable, using normal, low, or high based on normal range values. The visit window definition is also added in the appendix.

A small portion of the data may not go through source data verification (SDV) process due to the COVID-19 pandemic. The non-SDV'd data will be flagged in listings.

5. DEFINITIONS

5.1. Efficacy

5.1.1. Primary Endpoint(s)

Pharmacokinetic/Pharmacodynamic parameters (trough and peak) at baseline and Weeks 2, 10, 18, and 26

- PK: maximum serum concentration (C_{max}), trough serum concentration (measured at end of dosing interval at steady state; C_{trough}), accumulation ratio
- PD: change in free C5 concentrations and in chicken red blood cell (cRBC) hemolytic activity over time.

5.1.2. Secondary Endpoints

The secondary endpoints include:

- Percentage change in LDH from baseline to Day 183 (Week 26)
- Transfusion avoidance (TA), defined as the proportion of patients who remain transfusion-free and do not require a transfusion through Day 183 (Week 26)
- Change in quality of life (QoL), as measured by Pediatric Functional Assessment of Chronic Therapy (FACIT) Fatigue questionnaire (patients ≥ 5 years of age), from baseline to Day 183 (Week 26)
- Proportion of patients with stabilized hemoglobin, defined as avoidance of a ≥ 2 g/dL decrease in hemoglobin level from baseline in the absence of transfusion through Day 183 (Week 26)
- Percentage change in free hemoglobin from baseline to Day 183 (Week 26)
- Proportion of patients with breakthrough hemolysis, defined as at least one new or worsening symptom or sign of intravascular hemolysis (fatigue, hemoglobinuria, abdominal pain, shortness of breath [dyspnea], anemia, major adverse vascular event [MAVE, including thrombosis], dysphagia, or erectile dysfunction) in the presence of elevated LDH as follows:
 - For patients who enter the study naïve to complement inhibitor treatment, elevated LDH $\geq 2 \times$ ULN after prior LDH reduction to $< 1.5 \times$ ULN on therapy
 - For patients who enter the study stabilized on eculizumab treatment, elevated LDH $\geq 2 \times$ ULN.

5.2. Pharmacokinetic/Pharmacodynamic

Total C5 concentrations over time will be assessed besides the PK/PD endpoints specified in Section 5.1.1.

5.3. Safety

The safety and tolerability of ALXN1210 will be evaluated from baseline to Week 26 and throughout the Extension Period by AEs and serious adverse events (SAEs), physical examinations, vital signs, physical growth (height, weight, and head circumference [the latter only in patients who are ≤ 3 years of age]), electrocardiograms (ECGs), and laboratory assessments. The proportion of patients who develop antidrug antibodies (ADAs) will also be assessed.

5.3.1. Adverse Events (AEs)

An AE is defined as any unfavorable and unintended sign (eg, including an abnormal laboratory finding), symptom, or disease temporally associated with the use of a medicinal product or procedure, whether or not considered related to the medicinal product or procedure, which occurs during the course of the clinical study.

Exacerbations of a chronic or intermittent pre-existing condition, including either an increase in frequency and/or intensity of the condition, are all to be considered AEs.

All AEs will be graded according to criteria from CTCAE v4.03, published 14 Jun 2010 or higher.

Grade	Description
Grade 1	Mild; asymptomatic or mild symptoms; clinical or diagnostic observations only; intervention not indicated
Grade 2	Moderate; minimal, local or noninvasive intervention indicated; limiting age-appropriate instrumental ADL ^a
Grade 3	Severe or medically significant, but not immediately life-threatening; hospitalization or prolongation of hospitalization indicated; disabling; limiting self-care ADL ^b
Grade 4	Life-threatening consequences; urgent intervention indicated.
Grade 5	Death related to AE.

^a Instrumental ADL refers to preparing meals, shopping for groceries or clothes, using the telephone, managing money, etc.

^b Self-care ADL refers to bathing, dressing and undressing, feeding self, using the toilet, taking medications, and not bedridden.

Abbreviations: ADL = activities of daily living; AE = adverse event

Adverse events are further defined in Protocol [Section 11.7](#).

5.3.2. Vital Signs

Vital sign measurements will be taken after the patient has been resting for at least 5 minutes, and will include systolic and diastolic blood pressure (BP; millimeters of mercury [mmHg]), heart rate (beats/minute), respiratory rate (breaths/minute), and temperature (degrees Celsius [°C] or degrees Fahrenheit [°F]).

5.3.3. Laboratory Assessments

Samples for serum pregnancy, hematology, chemistry, coagulation, and urinalysis will be collected (See Appendix D of the protocol for a listing of all clinical laboratory parameters). An alternative blood sampling schedule for infants, for whom less blood volume should be collected, must be used as detailed in the laboratory manual. If a suspected event of breakthrough

hemolysis occurs, an unscheduled visit must take place at which a sample is collected for analysis of LDH and PK/PD by the central laboratory. A central laboratory will be used to evaluate all laboratory assessments.

5.3.4. Physical Examination

A physical examination will include the following assessments: general appearance; skin; head, ear, eye, nose, and throat; neck; lymph nodes; chest; heart; abdominal cavity; limb; central nervous system; and musculoskeletal system. An abbreviated physical examination consists of a body system relevant examination based upon Investigator judgment and patient symptoms. Physical growth (height, weight and head circumference [the latter only in patients ≤ 3 years of age]) will be assessed.

5.3.5. Electrocardiograms (ECGs)

For each patient, single 12-lead digital ECGs will be collected. PR, RR, and QT will be measured, and QT interval will be corrected for heart rate using Fridericia's formula (QTcF).

5.3.6. Immunogenicity

Blood samples will be collected to test for presence and titer of ADAs to ALXN1210 in serum prior to study drug administration. Further characterization of antibody responses may be conducted as appropriate, including binding and neutralizing antibodies, PK/PD, safety, and activity of ALXN1210.

6. DATA SETS ANALYZED (STUDY POPULATIONS)

6.1. Safety Set

The Safety Set will consist of all patients who received at least 1 dose of ALXN1210; this population will be used for the safety analysis.

6.2. PK Analysis Set and PD Analysis Set

The PK analysis set will consist of all patients in the Safety Set who have evaluable PK data used to derive PK parameters for ALXN1210. The PK analysis set will be used for PK summaries. The PD analysis set will consist of all patients in the Safety Set who have evaluable PD data. The PD analysis set will be used for all PD summaries.

6.3. Full Analysis (FAS)

The Full analysis set (FAS) will consist of all patients in the Safety Set with a baseline and 1 secondary endpoint measurement post-first ALXN1210 dose.

7. STATISTICAL ANALYSIS

All data collected in this study will be documented using summary tables, figures, and data listings. For categorical variables, frequencies and percentages will be presented by naïve, previously eculizumab-treated patients and total; for continuous variables, descriptive statistics (n, mean, median, standard deviation [SD], minimum, maximum) will be presented by naïve, previously eculizumab-treated patients and total.

Descriptive statistics for PK parameters will include the number of observations, mean, SD, coefficient of variance (CV), median, minimum, maximum, geometric mean, and geometric %CV.

Clinical central laboratory samples that meet the definition of TTH will be identified and all potassium, ALT, AST, magnesium, phosphorous, and LDH samples affected by TTH will be excluded from analysis of all efficacy and safety endpoints, with the exception that the LDH values will be used for the qualification of breakthrough hemolysis. The TTH samples from the central lab will be defined as having serum potassium ≥ 6 mmol/L and LDH $\geq 2 \times$ ULN.

A small portion of the data may not go through source data verification (SDV) process due to the COVID-19 pandemic. The non-SDV'd data will be flagged in listings.

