8.1. Inclusion Criteria

Patients are eligible for enrollment in the study only if they meet all of the following criteria and none of the exclusion criteria:

- 1. Male and female patients < 18 years of age and weighing ≥ 5 kg at the time of consent.
- 2. Documented diagnosis of PNH, confirmed by high-sensitivity flow cytometry evaluation (Borowitz, 2010) of red blood cells (RBCs) and white blood cells (WBCs), with granulocyte or monocyte clone size of \geq 5%.
- 3. For patients not currently treated with eculizumab, presence of 1 or more of the following PNH-related signs or symptoms within 3 months of Screening: fatigue, hemoglobinuria, abdominal pain, shortness of breath (dyspnea), anemia, history of a major adverse vascular event (including thrombosis), dysphagia, or erectile dysfunction; or history of packed red blood cell (pRBC) transfusion due to PNH.
- 4. Lactate dehydrogenase (LDH) values at Screening as follows:
 - a. For patients not currently treated with eculizumab, LDH level $\geq 1.5 \times \text{ULN}$.
 - b. For patients who are currently taking eculizumab, LDH $\leq 1.5 \times$ ULN (sample must be obtained on a scheduled eculizumab-dosing day prior to dose administration [ie, at trough eculizumab level] and analyzed by the central laboratory).
- 5. To reduce the risk of meningococcal infection (*N meningitidis*), all patients must be vaccinated against meningococcal infections within 3 years prior to, or at the time of, initiating study drug. Patients who initiate study drug treatment less than 2 weeks after receiving a meningococcal vaccine must receive treatment with appropriate prophylactic antibiotics until 2 weeks after vaccination. Patients who cannot be vaccinated must receive antibiotic prophylaxis for the entire treatment period and for 8 months following last dose.
- 6. Patients must have been vaccinated against *Haemophilus influenzae* type b (Hib) and *Streptococcus pneumoniae* according to national and local vaccination schedule guidelines, as appropriate.
- 7. Female patients of childbearing potential (ie, have achieved menarche) and male patients with female partners of childbearing potential must follow protocol-specified guidance for avoiding pregnancy while on treatment and for 8 months after last dose of study drug.

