7.3.3. Other Safety

7.3.3.1. Analyses for Laboratory Tests

Descriptive statistics by visit will be presented for each central laboratory parameter and for changes from baseline (continuous variables), by naïve, previously eculizumab-treated patients, and total. baseline is defined as the last non-missing assessment value prior to the first ALXN1210 infusion. Shift tables over time will be presented for all central laboratory values, where applicable, using normal, low, or high based on normal range values. For purposes of analyses, laboratory results based upon standardized units will be used. Individual patient plots as well as box plots will be presented for the following central lab parameters: hemoglobin, haptoglobin, hematocrit, reticulocytes, LDH, bilirubin, direct bilirubin, creatinine, AST, ALT, and GGT.

All central and local laboratory data will be presented in by-patient listings.

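### The table-top hemolysis rule removes potassium from the laboratory safety tables partly on its own value, so a true potassium ≥ 6 mmol/L with LDH ≥ 2 × ULN drops out of the descriptives and shift tables

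*SAP*

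**What the plan says.** SAP section 7 gives a two-part definition: "The TTH samples from the central lab will be defined as having serum potassium ≥ 6 mmol/L and LDH" of at least 2 × ULN. No other criterion is attached. The consequence is that "all potassium, ALT, AST, magnesium, phosphorous, and LDH samples affected by TTH will be excluded from analysis of all efficacy and safety endpoints". One carve-out applies: LDH from a flagged sample still counts when a breakthrough event is being qualified. SAP 4.2 states the same rule and gives the reasoning. Potassium is normal in PNH hemolysis, whereas "for samples affected by TTH both potassium and LDH are markedly and proportionally increased". Marked hyperkalemia therefore "differentiates TTH (in vitro) from PNH hemolysis (in vivo), and is not clinically significant". SAP 4.2 also gives the only frequency, from two other Phase 3 studies of the programme: "up to 1% of central laboratory chemistry samples undergo in vitro erythrocyte lysis or table top hemolysis (TTH) caused by sample mishandling".

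For laboratory safety, SAP 7.3.3.1 plans by-visit descriptives and changes from baseline for each central parameter, and adds: "Shift tables over time will be presented for all central laboratory values, where applicable, using normal, low, or high based on normal range values". Box plots and individual plots are planned for a list of parameters that includes ALT and AST but not potassium, magnesium or phosphorus. The same section lists every central and local result by patient. Protocol 11.4 has laboratory changes of clinical significance recorded as adverse events. It defines clinical significance as medical relevance together with a resulting change in care.

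**The concern.** An exclusion rule for a safety table should not depend on the value that the table reports. Here potassium is one of the two classifiers and also one of the six analytes removed. If the flag is wrong for a sample, the tables lose a high potassium because it was high, and they lose the accompanying liver enzymes, magnesium and phosphorus as well.

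The second condition, LDH of at least 2 × ULN, gives no protection in a child who is hemolysing at that level. Such values are plausible in this trial. Protocol criterion 4a reads "For patients not currently treated with eculizumab, LDH level" of at least 1.5 × ULN at Screening, and breakthrough hemolysis is defined with LDH of at least 2 × ULN. Safety is a stated objective. With about a dozen patients split into naïve and eculizumab-treated groups, one value can set a maximum or fill a shift-table cell.

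**Working it through.** The documents derive no figure for this rule, so there is none to reproduce. The check has three parts.

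**1. What the rule removes.** Applying potassium ≥ 6 mmol/L and LDH ≥ 2 × ULN to a grid of values:

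| Potassium (mmol/L) | LDH 1.0, 1.5 or 1.99 × ULN | LDH 2.0 or 5.0 × ULN |
|---|---|---|
| 5.4, 5.9 | kept | kept |
| 6.0, 6.5, 7.0 | kept | excluded |

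Once LDH reaches 2 × ULN, every central potassium of 6 mmol/L or more is removed, whether true or artefactual. A raised potassium below 6 stays at any LDH, and any potassium stays when LDH is below 2 × ULN.

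**2. Rationale against definition.**
- SAP 4.2 argues from a proportional rise of potassium and LDH. The definition sets two separate cut-offs and tests no proportionality. It asks for no hemolysis index, repeat sample or record of mishandling.
- The statement that potassium is normal in PNH hemolysis supports the view that PNH hemolysis does not itself produce the flagged value. It says nothing about hyperkalemia from another cause in a child whose LDH is already high.
- The flag is not treated as conclusive throughout. The LDH of a flagged sample may still qualify a breakthrough event, while the same sample's potassium, ALT and AST are set aside as artefact.
- SAP 4.2 describes marked hyperkalemia as above 6 mmol/L, but the definition uses at or above 6. Only a value of exactly 6.0 is affected.

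**3. Scale.**
- Patients: 12, because SAP section 4 limits this SAP to the report prepared after 12 patients are enrolled.
- Chemistry samples per patient: 9 (Screening and Days 1, 15, 43, 71, 99, 127, 155 and 183; SAP Table 4).
- Artefact rate r: 1% is the SAP's upper figure. The lower value of 0.25% is my assumption. Samples are taken as independent.
- Formulas: N = patients × samples per patient; expected flagged samples = N × r; chance of at least one = 1 − (1 − r)^N.

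| Samples counted | N | r | Expected flagged | Chance of at least one |
|---|---|---|---|---|
| All scheduled | 12 × 9 = 108 | 1% | 108 × 0.01 = 1.08 | 1 − 0.99^108 = 66% |
| All scheduled | 108 | 0.25% | 108 × 0.0025 = 0.27 | 1 − 0.9975^108 = 24% |
| Post-baseline only | 12 × 7 = 84 | 1% | 84 × 0.01 = 0.84 | 1 − 0.99^84 = 57% |
| Post-baseline only | 84 | 0.25% | 84 × 0.0025 = 0.21 | 1 − 0.9975^84 = 19% |

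These are counts of artefacts. The documents give no rate of true potassium ≥ 6 mmol/L, so the number of true values removed cannot be computed and may be zero.

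**The case against.** The strongest defence is that the rule is prespecified, reasoned and disclosed. Potassium is in the definition because, on the SAP's account, it separates lysis in the tube from disease. In so small a study, one artefact left in could dominate a by-visit mean or maximum. The rule governs reporting and not care, since investigators receive the laboratory reports and the DMC reviews safety data. All of this stands. It justifies having an exclusion, but it does not justify showing only the version with the exclusion applied.

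A reader might infer more than the documents support, in three ways.

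- *That real hyperkalemia could not appear in any safety summary.* It could. A change judged clinically significant is recorded as an adverse event and counted by SOC and PT (SAP 7.3.2.2), and nothing removes an event because its sample was flagged. The value also appears in the listings. The adverse-event route is incomplete, because it depends on the investigator's judgement and a change in care. The listings carry no planned TTH flag; the only listing flag in section 7 is for data without source verification.
- *That the LDH condition never discriminates in this disease.* It does whenever LDH is below 2 × ULN. Criterion 4a is set at 1.5 and not 2, and criterion 4b requires LDH of at most 1.5 × ULN in patients on eculizumab. Protocol 5.1.1 describes a rapid, sustained fall in LDH on treatment.
- *That the tables are spared about one false value at the price of hiding many true ones.* With no rate of true hyperkalemia in the documents, that comparison cannot be made.

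**Conclusion.** The point holds in a limited form. A true central potassium of 6 mmol/L or more with LDH of at least 2 × ULN is removed, by construction, from the laboratory descriptives and shift tables, along with four other safety analytes from the same sample. It can then be seen only in listings or, conditionally, as an adverse event. The stated rationale does not cover hyperkalemia from a cause other than PNH hemolysis, and the definition does not test the proportional rise on which the rationale relies.

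The likely number of flagged samples is small, about 0.3 to 1.1 in the 12-patient report. That range assumes a rate of 0.25% to 1%, independent samples, and that the rate seen in the other two studies carries over to children. This does not affect the LDH or breakthrough hemolysis endpoints. I rate it a cheap improvement and not a flaw that threatens the study's conclusions.

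**What to change.** Keep the exclusion for the LDH efficacy endpoint. In SAP 7.3.3.1, present the potassium, ALT, AST, magnesium and phosphorus descriptives and shift tables, and the planned ALT and AST plots, twice: with all central samples, and without TTH-flagged samples. Report the number of flagged samples by visit and by stratum (naïve, previously eculizumab-treated, total), and mark them in the by-patient listings.

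The cost is a few sentences in the SAP and a second version of the outputs for five analytes. It needs no new data and no change in study conduct. The downside is that about one likely artefact may appear in the all-samples version, where the label and the paired table let a reader discount it.

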5.1. Benefits and Risks Assessment

5.1.1. Potential Benefits

As described above, PNH is an ultra-rare, progressive, debilitating, and life-threatening disease, driven by chronic uncontrolled complement activation. The resulting inflammation and cellular damage lead to systemic complications, principally through intravascular hemolysis and thrombophilia (Brodsky, 2014; Socie, 1996). Chronic intravascular hemolysis due to continuous activation of the complement pathway leads to the release of free hemoglobin, nitric oxide consumption and persistent smooth muscle cell contraction, chronic anemia, and an increased risk of severe thromboembolism. Patients with PNH are at risk of substantial morbidity and mortality and altered quality of life (QoL). The current standard of care for the treatment of PNH is eculizumab (Soliris®), a recombinant humanized monoclonal antibody (mAb) that binds to human complement component 5 (C5) and inhibits the activation of terminal complement.

The efficacy and safety of eculizumab for the treatment of PNH are well established. The approved dosage regimen for eculizumab for PNH involves 4 weekly induction doses, followed by maintenance doses administered every 2 weeks starting at Week 5.

Given that PNH is a chronic disease, the current eculizumab regimen may significantly affect patients, many of whom have to miss days of work or school to accommodate treatment. In some cases, patients may refuse treatment or may be unable to comply with the treatment frequency of eculizumab. Practice survey research supports the assumption that the less frequent infusions associated with ALXN1210 will have a positive impact on daily life for patients and their caregivers.

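### The table-top hemolysis rule removes six chemistry analytes but says nothing about free hemoglobin from the same visit, although its percentage change to Day 183 is a secondary endpoint.

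*SAP*

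**What the plan says.** SAP section 4.2 explains that in the two adult phase 3 studies "up to 1% of central laboratory chemistry samples undergo in vitro erythrocyte lysis". On causes it says: "The reasons for TTH vary and include delayed or improper centrifugation and traumatic blood draws". It adds that red cells from patients with PNH are more prone to mechanical lysis, and it gives the reason for acting: "Hemolysis results in release of RBC contents including LDH, potassium, and AST".

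The operative rule is in section 7. A central-laboratory sample is flagged when serum potassium is at least 6 mmol/L and LDH is at least 2 × ULN. For flagged samples, "all potassium, ALT, AST, magnesium, phosphorous, and LDH samples affected by TTH will be excluded from analysis of all efficacy and safety endpoints". The one exception is that LDH may still be used to qualify breakthrough hemolysis.

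Free hemoglobin appears in neither section. SAP 5.1.2 makes its percentage change from baseline to Day 183 a secondary endpoint. SAP 7.2.2 summarizes it by observed case and by LOCF at every visit up to Day 183 and plots means with 95% CIs. Its baseline is the last non-missing pre-dose value. None of these rules screens for hemolyzed draws. For LDH, by contrast, the baseline is an average of the pre-dose values.

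**The concern.** The SAP's reason for the exclusion is that lysed red cells spill their contents into the sample. Hemoglobin is red-cell content. Protocol 5.1.1 says of hemolysis inside the vessels that it "leads to the release of free hemoglobin"; neither document says the same of lysis in the tube, but it follows from the mechanism in SAP 4.2.

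Followed as written, the plan can discard LDH from a visit as an artefact and still analyze free hemoglobin from that visit as efficacy data. Two secondary endpoints that both measure hemolysis would then be treated differently, with no reason given.

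The study is small, so one value counts. About 13 patients are split into naïve and previously eculizumab-treated groups, and means are reported. The single-value baseline gives free hemoglobin less protection than LDH has. Under LOCF, an affected value can also stand in for a missing later one.

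**Working it through.** The plan gives no figure for this effect, so there is nothing to reproduce. The calculation below only shows scale.

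**Inputs from the documents**
- Planned enrollment: about 13 (Protocol 14.2).
- TTH rate: up to 1% of chemistry samples, all causes, in the adult studies (SAP 4.2).
- Location of free hemoglobin: hematology panel (Protocol Table 1 and Appendix D). LDH and potassium are in clinical chemistry.
- Timing: both panels are scheduled at every visit in Table 1 and are taken before dosing on dosing days.

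**Assumptions, not in the documents**
- The 1% chemistry rate applies to free-hemoglobin samples, and draws are independent. A rate of 0.25% is the lower comparison. It would arise if one flagged draw in four also affected the hematology sample (0.01 × 0.25 = 0.0025).
- A subgroup of 5. The documents give no planned split between naïve and previously treated patients.
- An affected value is inflated k-fold, with k = 2 to 5.

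**Chance of at least one affected Day 183 value**, 1 − (1 − p)^n:
- n = 13, p = 1%: 1 − 0.99^13 = 12.2%.
- n = 13, p = 0.25%: 1 − 0.9975^13 = 3.2%.
- n = 5, p = 1%: 1 − 0.99^5 = 4.9%.

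The 13 baseline values carry the same chance as the 13 Day 183 values. Pooling all 26 gives 1 − 0.99^26 = 23%, but the two kinds of error act in opposite directions.

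**Shift in the mean percent change from one affected value, true change zero in everyone**
- Day 183 inflated: (k − 1)/n × 100. With n = 5 this is +20 (k = 2) to +80 (k = 5) points. With n = 13 it is +7.7 to +30.8.
- Baseline inflated: (1/k − 1)/n × 100. With n = 5 this is −10 to −16 points. With n = 13 it is −3.8 to −6.2. A false fall from baseline favors the drug.

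**Same check with an assumed true change of −50% in everyone and k = 5**
- Day 183 inflated: the affected patient shows (0.5 × 5 − 1) × 100 = +150%. With n = 5 the mean is (4 × (−50) + 150)/5 = −10%. With n = 13 it is (12 × (−50) + 150)/13 = −34.6%.
- Baseline inflated: the affected patient shows (0.5/5 − 1) × 100 = −90%. The mean is −58% with n = 5 and −53.1% with n = 13.

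In each of these groups the median does not move, because only one patient departs from the common value.

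**The case against.** The strongest objection is that the flag describes a different sample. TTH was observed in chemistry samples and is defined by two chemistry analytes. Protocol 11.4 leaves collection and processing to the Laboratory Manual, which is not among the documents. Of the causes listed, "delayed or improper centrifugation and traumatic blood draws", a centrifugation fault need not touch a separately handled hematology tube.

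This stands, and it limits the point. A reader might infer that a traumatic draw spoils every tube from the venipuncture, so that free hemoglobin at a flagged visit is contaminated and must come out of the main analysis. The documents do not say so. A shared venipuncture is plausible, since both panels are taken at the same visits and Appendix A of the protocol allows at most three attempts per day, but it is not established. If the tubes are separate and unaffected, mandatory exclusion would delete valid data: one value in an assumed group of 5 is 20% of that group.

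The second objection is that little depends on this. The study is descriptive, medians, minima and maxima are reported, and by-patient listings cover all secondary endpoints, so a gross outlier would be visible. That also stands. A reader might say that one artefact dominates the endpoint, but this can be true only of the mean. It remains a gap because a visible outlier with no pre-specified rule invites a decision after the result is known.

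**Conclusion.** The gap is real and modest. The SAP should state how free hemoglobin is handled when the chemistry sample from the same visit is flagged. No primary endpoint, sample size or decision rule is affected.

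The size depends on assumptions. If the upper-limit rate carries over and draws are independent, the chance of at least one affected Day 183 value is about 12% among 13 patients, about 3% at 0.25%, and about 5% within an assumed group of 5. In that group of 5, one value inflated 2- to 5-fold moves the mean by +20 to +80 points. An inflated baseline moves it by −10 to −16 points, towards the drug.

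A reader might pair the pooled 23% with the +80 points. That is not supported: the 23% mixes baseline and Day 183 errors across all 13 patients, whereas the +80 needs a Day 183 error within the group of 5, for which the matching chance is about 5%.

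**What to change.** In SAP 4.2, 7 and 7.2.2, flag free hemoglobin values from any visit whose chemistry sample meets the TTH definition. Pre-specify a summary of change and percent change in free hemoglobin, by observed case and LOCF, without the flagged values, beside the summary with all values. Apply the flag to baseline visits as well as later ones.

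Check the Laboratory Manual. If free hemoglobin comes from the same tube as chemistry, add it to the exclusion list and make the summary with all values the sensitivity analysis.

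The cost is one programming flag and one extra table row. With the side-by-side summary, no data are discarded.
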